8.6. Pharmacokinetics

Pharmacokinetic samples will be collected in subjects who experience virologic failure in order to determine drug levels at the time of viral rebounds.

Pregnant participants will have additional PK samples collected during the duration of the pregnancy. See [Appendix 8](#) for details.

8.7. Pharmacodynamics

Pharmacodynamic parameters are not evaluated in this study.

8.8. Genetics

Genetics are not evaluated in this study.

8.9. Biomarkers

Biomarkers are not evaluated in this study.

8.10. Health Economics

Health Economics/Medical Resource Utilization and Health Economics parameters are not evaluated in this study.

9. STATISTICAL CONSIDERATIONS

9.1. Statistical Hypotheses

No formal hypothesis testing is planned.

9.2. Sample Size Determination

As described above, the study size is based on practical considerations in terms of feasibility of enrolling an adequate number of sites on each intervention balanced with the desire to have interventions tested across several types of investigative sites: University Setting, Private Practice and Ryan White Clinic.

The primary consideration for study sizing is to obtain in-depth qualitative site level feedback via interviews of site personnel (treating clinician, nurses, administrators).

Additionally, this study is a single arm, open label interventional study, whereby patients at each site will receive the same intervention of the CAB + RPV LA ARV regimen and additional site facilitation to support the implementation of this regimen in their practice setting.

The primary endpoint is change from baseline to the study Month 12 injection visit in site survey responses for acceptability, appropriateness and feasibility, as described above (cross-reference and provide published citation). This survey includes a likert scale of

response ranging from 1 to 5, with higher values representing better outcomes. Although adequate prior information on expected responses are unavailable, it is expected that the standard deviation of change from baseline is 0.50.

9 sites will allow for estimation of paired mean change from baseline of 0.55 (half-width of the 95% confidence interval) using a two-sided confidence interval based on the normal distribution and assumed standard deviation of 1.

For subject level outcomes, the primary outcome will also be survey responses as described above (reference surveys). 135 subject pairs (average of 15 per site) will allow for estimation of paired mean change from baseline of 0.17 (half-width of the 95% confidence interval) using a two-sided confidence interval based on the normal distribution and assumed standard deviation of 1.

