Unintended consequences refer to outcomes that are not anticipated and intended at the time of intervention implementation; they can be both positive (e.g. improved job satisfaction) and negative (e.g. increased workload for healthcare professional). During the semi-structured stakeholder interviews, we will ask if there were any unintended consequences that were not anticipated (i.e. Yes or No), if they were positive or negative and specifically what were they.

Disclosure Statement: This is a single group, open-label, interventional treatment study to assess the implementation of a new therapeutic strategy for HIV infection.

Number of Participants:

Approximately 9 sites will be included in this study and will be allowed two months to enrol up to 15 patient study participants each. Additional time for recruitment of patient study participants (up to an additional two months) may be allowed depending upon the site activation and enrollment rate. Fifteen patient study participants per site is intended as a reasonable number to provide clinic staff adequate exposure to implement the CAB + RPV LA regimen so that they can describe the challenges and practical limitations experienced during initial implementation of CAB + RPV LA. Fifteen patient study participants per site may also yield enough recurring office visits at clinics to necessitate alternate approaches to successful injection implementation beyond typical clinic practice. Therefore, the maximum number of patients included in this study is anticipated to be approximately 135.

Staff study participants from each site (physician/ PCP, nurse/medication administration personnel, administrator/clinic manager) will also take part in this study, including participation in surveys, interviews and facilitation calls.

Intervention Groups and Duration:

Informed consent must be obtained prior to any study procedures, including any Day 1 assessment.

Patient study participants

All patient study participants will complete the screening phase of up to 21 days prior to Day 1 during which all clinical and laboratory assessments of eligibility must be performed and reviewed. Participants may be re-screened twice. Participants who are

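### Section 9.2 gives a site-level 95% half-width of 0.55, but its own inputs give 0.65, and it states two different SDs for the site-level change

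*Protocol*

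**What the plan says.** Section 9.2 (Sample Size Determination) names the primary endpoint as the change from baseline to Month 12 in site survey responses for acceptability, appropriateness and feasibility, scored 1 to 5. It concedes that prior information is inadequate and then gives a planning value: "it is expected that the standard deviation of change from baseline is 0.50".

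The next paragraph turns the number of sites into a precision: "9 sites will allow for estimation of paired mean change from baseline of 0.55 (half-width of the 95% confidence interval"), obtained "using a two-sided confidence interval based on the normal distribution and assumed standard deviation of 1".

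The paragraph after that makes the parallel statement for patients, with the same method and the same SD of 1: "135 subject pairs (average of 15 per site) will allow for estimation of paired mean change from baseline of 0.17".

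The site count agrees with the design description in Section 1.3, under Number of Participants: "Approximately 9 sites will be included in this study". Section 9.1 adds: "No formal hypothesis testing is planned". Section 9.4 summarises the survey data descriptively, with 95% confidence intervals as appropriate.

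**The concern.** The site-level sentence supplies every input needed to check it: nine sites, two-sided 95%, normal distribution, SD 1. The half-width it prints does not follow from them. Separately, the SD in that sentence is twice the one announced as expected in the paragraph before. Nothing says that SD 1 is a conservative choice, or that the two values refer to different quantities.

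The study tests no hypothesis, so the width of the confidence interval is the only quantitative measure of what nine sites can show on the primary endpoint. This sentence is the only place where the protocol gives that width. A reader judging whether a shift on a 1 to 5 scale could be seen gets a figure that is wrong under one of the stated SDs and unrelated to the other.

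**Working it through.** **Inputs, all from Section 9.2:** n = 9 sites; two-sided 95%, so z = 1.960; SD = 1 in the precision sentence; SD = 0.50 in the paragraph before; stated half-width 0.55. For patients: n = 135, SD = 1, stated half-width 0.17.

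**Formula:** half-width = quantile × SD / √n.

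**Step 1: the plan's own site-level figure.** 1.960 × 1/√9 = 0.653. The plan prints 0.55, so it does not reproduce. The ratio is 0.653/0.55 = 1.19.

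**Step 2: the companion figure, as a control on the formula.** 1.960 × 1/√135 = 0.169, which rounds to the printed 0.17. The formula and quantile are therefore read as the protocol intends, and the site-level figure is the one that departs.

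**Step 3: can another reading produce 0.55?**

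| Reading | Half-width |
|---|---|
| n = 9, SD 1, 95%, normal (as stated) | 0.653 |
| n = 9, SD 1, 95%, t on 8 df (2.306) | 0.769 |
| n = 9, SD 0.50, 95%, normal | 0.327 |
| n = 9, SD 0.50, 95%, t on 8 df | 0.384 |
| n = 9, SD 0.50 × √2, 95%, normal | 0.462 |
| n = 9, SD 0.50 × √2, 95%, t on 8 df | 0.544 |
| n = 27 (three staff at each of nine sites), SD 1, 95%, normal | 0.377 |
| n = 9, SD 1, 90% two-sided, normal (1.645) | 0.548 |

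The √2 rows treat 0.50 as the SD of a single uncorrelated measurement. The protocol calls it the SD of the change, and the nearest result rounds to 0.54. Of these readings only the last rounds to 0.55, and it contradicts the stated 95%.

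**Step 4: what would make 0.55 true at 95% with the stated method.** With SD 1, n = (1.960/0.55)² = 12.7, so 13 sites. With nine sites, SD = 0.55 × 3/1.960 = 0.84. On the t distribution the corresponding values are 16 sites (15 give 0.554, 16 give 0.533) and an SD of 0.55 × 3/2.306 = 0.72. None of these is in the protocol.

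**Step 5: effect of the SD conflict.** With the normal quantile, SD 1 gives 0.65 and SD 0.50 gives 0.33, a factor of two. The printed 0.55 lies between them and is correct for neither.

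**The case against.** The strongest reply is that nothing depends on the number. Section 9.2 says that size was set by feasibility and by the wish for in-depth qualitative feedback from site personnel, and Section 1.3 justifies fifteen patients per site by clinic exposure. No hypothesis is tested, and the reported interval will be computed from observed data whatever the planning sentence says. This stands. It limits the severity and means that the site count need not change, but it does not make the sentence correct.

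Four stronger readings are tempting, and the protocol does not support them.

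- *The study is less precise than promised.* That follows only under SD 1. Under the SD called expected, 0.33 (or 0.38 with t) is narrower than 0.55. Since the protocol does not say which SD governs, the direction of the error is open.
- *The two figures were computed at different confidence levels.* The match of 0.55 to 1.645/3 makes this plausible, but it is an inference; the protocol labels the interval 95%.
- *Using a normal quantile is itself an error.* The protocol openly states the normal basis for a planning value with an assumed SD. With nine sites and an SD to be estimated, that is an optimistic approximation rather than an arithmetic mistake. Section 9.4 does not fix the distribution for the final intervals.
- *The patient-level figure must also change.* The SD of 0.50 is introduced alongside the site survey endpoint. A site's change and an individual patient's change need not share an SD, and the patient figure is right for the SD it states.

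**Conclusion.** The point holds, at moderate severity. Under the protocol's stated inputs the site-level 95% half-width is 0.65, not 0.55: the stated value is about 16% too small, or equivalently the interval is about 19% wider than stated. This needs no assumption beyond the inputs in the sentence itself.

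The SDs of 0.50 and 1 for the site-level change are a separate defect. Until one is chosen, the planned half-width is either 0.33 or 0.65 on the normal basis, or 0.38 or 0.77 on t with 8 degrees of freedom. The t values assume nine sites contributing one change each and an SD estimated from those nine values.

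**What to change.** In Section 9.2, state one SD for the site-level change from baseline and the reason for it. Then restate the half-width to match:

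- SD 1: 0.65 (normal), preferably with 0.77 (t, 8 df) alongside.
- SD 0.50: 0.33 (normal), preferably with 0.38 (t, 8 df) alongside.

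Keep the label at 95% two-sided. If a 90% interval was intended, say so; the 0.55 would then be right for SD 1.

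Leave the patient-level sentence alone unless the sponsor also intends SD 0.50 for patients, in which case 0.17 becomes 1.960 × 0.50/√135, about 0.08.

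The cost is a wording change in one section. The number of sites, the data collected and the planned summaries are unaffected. The stated precision becomes less favourable if SD 1 is kept and more favourable if SD 0.50 is adopted, which is why the reason for the choice should be given.

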Enrollment of Staff Study Participants: Investigational sites will be selected and staff study participants (lead HIV care providers (HCPs), Nurses/staff performing CAB + RPV LA injections, and administrators/clinic managers) will be identified prior to study commencement. Upon study initiation, clinical sites will have up to 2 months to engage and enrol up to 15 patient study participants into this study. Key objectives of this study relate to the delivery of the CAB + RPV LA regimen at a clinic, including the learning process clinic staff will undergo for this paradigm-changing regimen. One of the goals is to facilitate shared learnings across clinics in order to drive successful implementation, and this will be conducted through the short-term facilitation calls with study personnel. Thus, it is necessary for participating sites to initiate and complete enrolment concurrently within a short time frame. A limited enrolment period of up to 2 months is proposed with a goal to have approximately 80% of participating clinics fully prepared to enrol at the time of study commencement. Adjustments to this time frame will be considered by the sponsor study team based upon study progress and may include an extension of the enrolment period for up to a maximum of 4 months; if the enrolment period is extended beyond 2 months, enrolment caps at individual sites may be raised beyond 15, up to the study maximum of 135 patient study participants.

All lead investigators, nurses/injectors, and/or administrators responsible for implementation will attend an in-person investigator meeting prior to study start. The purpose of this meeting is to educate healthcare staff on the CAB + RPV LA regimen, including the proper administration of the regimen, protocol requirements for all study participants, data collection methods and an overview of available support tools (toolkit). Additionally, an overview of the key protocol objectives and relevant implementation science elements will be reviewed.

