While a “toolkit” of supporting elements will be provided in this study, clinical sites will be allowed to choose how they will implement CAB + RPV LA delivery in their clinical setting (i.e. nurse visit during clinic hours, pre-post clinic hours, weekend hours, Tues/Thursday clinics, etc.) as well as to create and use their own clinic-developed resources. The delivery models chosen will be tracked by study staff and captured in the surveys and semi-structured interviews. Modifications made to the implementation process or approach during the study i.e. who administers the injection, timing of delivery of the injection, use of support materials, etc are permissible and encouraged in order to facilitate successful delivery of the CAB + RPV LA regimen. Investigators will inform the study team of their change and document the reasons why (step change).

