9.4. Statistical Analyses

As mentioned above, this study has both site- and subject-level outcomes and each outcome will be analyzed and summarized accordingly.

Survey Data:

Qualitative interview data will be summarized by Evidera and reported as part of the overall study results (CSR). Details of these analyses will be described in a separate analysis plan provided by Evidera or other CRO partner under GSK's oversight. Randomization will be used to assign patients from the PSP to qualitative interview group or to no interview group.

Quantitative data (site and subject level) will be summarized using descriptive statistics including 95% confidence intervals for primary and secondary endpoints, as appropriate. Data will be summarized by month of study/injection visit as actual values and change from baseline.

Responses will be summarized overall and by site type. Exploratory analyses will be undertaken to assess the variability of responses by factors including but not limited to site type, setting (urban, suburban, rural) and for subject level outcomes markers of demographic and baseline characteristics.

Clinical Safety and Efficacy data:

Given that this is an interventional clinical trial of an unapproved investigational product, standard analyses will be applied to summarize descriptively clinical adverse events, laboratory evaluations, virologic parameters and other outcomes.

All analyses performed will be described in the study Reporting and Analysis Plan which will be finalized and approved prior to database lock.

One interim analysis will be timed to provide preliminary data to inform the initial commercial availability of the CAB + RPV LA regimen. No formal criteria for stopping or amending the study based on the interim analysis are envisioned.

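### The patient-level half-width of 0.17 in Section 9.2 holds only if change scores are independent within the nine sites and all 135 patients give complete pairs; with plausible within-site correlation at the stated SD of 1 it is optimistic

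*Protocol*

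**What the plan says.** For patients, Section 9.2 states that "135 subject pairs (average of 15 per site) will allow for estimation of paired mean change from baseline of 0.17", and gives the basis as "using a two-sided confidence interval based on the normal distribution and assumed standard deviation of 1". Earlier in the same section, for the site survey, "it is expected that the standard deviation of change from baseline is 0.50". The section names the average site size but gives no intra-site correlation, design effect or allowance for missing pairs.

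On the site structure, Section 1.3 says "Approximately 9 sites will be included in this study", with about 135 patients as the study maximum. Section 9.2 says that "patients at each site will receive the same intervention of the CAB + RPV LA ARV regimen and additional site facilitation". Section 1.3 adds that "clinical sites will be allowed to choose how they will implement CAB + RPV LA delivery in their clinical setting". Section 7 says that withdrawn participants are not replaced.

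On the analysis, Section 3 makes the patient-rated Acceptability of Intervention Measure (AIM) and Intervention Appropriateness Measure (IAM) primary endpoints. Section 9.4 says "Quantitative data (site and subject level) will be summarized using descriptive statistics including 95% confidence intervals". It does not say how the intervals are computed and leaves the analyses to the Reporting and Analysis Plan. Section 9.1 plans no formal hypothesis test.

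**The concern.** Patients at one clinic are injected by the same few staff, under the delivery model which that clinic chose, and with the facilitation which it took up. How their acceptability and appropriateness ratings change between Month 1 and Month 12 may therefore be partly shared. If so, 135 patients in nine sites carry less information than 135 unrelated patients, and a half-width computed as if they were unrelated is too small.

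The protocol tests no hypothesis, so interval width is its only quantitative basis for the patient sample. A reader of Section 9.2 would expect the mean change to be known to within 0.17 on a 1-to-5 scale. An interval later computed on the same basis would also cover less than 95% if sites differ in their mean change. In addition, 135 complete pairs is the best case, because 135 is the enrolment maximum and withdrawals are not replaced.

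**Working it through.** **Inputs from the protocol.** n = 135 pairs, average site size m = 15, SD of change 1, two-sided 95% normal interval (Section 9.2); about 9 sites (Section 1.3). The ICC of the change scores is not given, so a range is assumed.

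**Step 1: reproduce the stated figure.**
- Half-width = 1.96 × SD/√n = 1.96 × 1/√135 = 0.1687, which rounds to 0.17.
- With t on 134 degrees of freedom it is 0.1702, also 0.17.

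The stated figure is therefore an independence calculation on 135 complete pairs.

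**Step 2: allow for site.** With equal site sizes, the design effect is DE = 1 + (m − 1) × ICC = 1 + 14 × ICC, and the half-width is q × SD × √(DE/135). The quantile q is 1.96 (normal), or 2.306 (t on 8 degrees of freedom, nine sites less one). If the interval is computed under independence as in Section 9.2, its actual coverage by normal theory is 2Φ(1.96/√DE) − 1. At SD 1:

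| Assumed ICC | DE | Effective n (135/DE) | Half-width, normal | Half-width, t on 8 df | Coverage of independence interval |
|---|---|---|---|---|---|
| 0.01 | 1.14 | 118 | 0.18 | 0.21 | 93% |
| 0.05 | 1.70 | 79 | 0.22 | 0.26 | 87% |
| 0.10 | 2.40 | 56 | 0.26 | 0.31 | 79% |

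For example, at ICC 0.05: √(1.70/135) = 0.1122; 1.96 × 0.1122 = 0.22; 2.306 × 0.1122 = 0.26.

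At ICC 0, DE = 1 and the half-width is 0.17, as stated.

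**Step 3: sensitivity to the SD.** If the SD of 0.50 given for the site survey applied to patients, the independence half-width would be 1.96 × 0.50/√135 = 0.084. Half the SD allows a design effect of 4 before the half-width returns to 0.1687, so ICC = (4 − 1)/14 = 0.21. On that SD, 0.17 would hold up to an ICC of about 0.21 with the normal quantile.

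Attrition is not quantified here, because the protocol gives no expected rate. Any loss of pairs widens the interval further.

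**The case against.** The strongest case against the point has four parts.

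- **The ICC is unknown and may be small.** The relevant ICC is that of within-patient change, so stable differences in level between sites cancel. All sites give the same regimen, the facilitation calls are held jointly for all clinics, and Appendix 10 describes the patient scales as rating the injection. This stands as a limit on the size: the protocol makes a site effect plausible but does not establish how large it is.
- **The SD is unsettled.** With 0.50 instead of 1, 0.17 survives a wide range of ICCs. This also stands. However, Section 9.2 computes 0.17 at SD 1, so the figure has to be judged there, and having two SDs in one section is itself a reason to clarify.
- **Little hangs on 0.17.** There is no test or success threshold, and sizing rests mainly on feasibility and qualitative site feedback. This limits the consequence to stated precision.
- **Interval methods belong to the Reporting and Analysis Plan.** A reader might infer that the planned 95% intervals are already too narrow. The protocol does not support that: Section 9.4 names no method. The coverage figures apply only if the intervals are computed as in Section 9.2.

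Three other inferences also go too far. One is that the half-width should be 0.20 even at ICC 0; that number, 2.306/√135, comes only from choosing 8 degrees of freedom. Another is that one or two sites will dominate the mean, because "enrolment caps at individual sites may be raised beyond 15"; that is a permission tied to extended enrolment within the same overall maximum, not a prediction. The last is that the staff precision figure needs the same correction; it is already based on nine sites, not on individual staff.

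**Conclusion.** The point holds for the stated precision. At the SD of 1 that Section 9.2 uses, 0.17 is correct only if change scores are independent within sites and all 135 patients give complete pairs. Any positive within-site correlation makes it optimistic. For assumed ICCs of 0.01 to 0.10 with equal sites of 15, the half-width is about 0.18 to 0.26 (normal) or 0.21 to 0.31 (t on 8 degrees of freedom). An interval computed under independence would cover about 93% down to 79%. The size rests on an ICC that the protocol does not give and on SD 1 being the right value for patients.

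This is a correction worth making, not a threat to the study: no decision rule uses 0.17, and the protocol does not show that the reported intervals will be wrong.

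**What to change.** In Section 9.2:
- state that 0.17 assumes independence within site, SD 1 and 135 complete pairs;
- give the half-width over a stated ICC range, for example the values in the table above;
- state which SD of change, 0.50 or 1, applies to patients.

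In the analysis plan, compute the patient-level AIM and IAM 95% intervals with a method that respects nine clusters, either a random site intercept or a cluster-robust variance with a small-sample correction. Report the estimated ICC.

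The cost is some wording and a few lines of code, and the intervals will be wider where sites differ. No extra patients or visits are needed.
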